•	To assess the effect of cotadutide versus placebo on circulating markers of hepatic inflammation	•	Change from baseline in liver enzymes including ALT and AST through Week 48
•	To assess the effect of cotadutide versus placebo on lipid profile and glycemic control	•	Change from baseline in triglycerides, LDL cholesterol, HDL cholesterol, non-HDL cholesterol, total cholesterol, and HbA1c through Week 48
•	To summarize the PK profile of cotadutide	•	Cotadutide PK exposure will be summarized and compared with prior data for consistency
•	To assess the effect of cotadutide versus placebo on liver stiffness	•	Change from baseline at Week 48 in:  LSM as assessed by FibroScan  Percentage CAP as assessed by FibroScan
•	To assess the effect of cotadutide versus placebo on disease-specific biomarkers	•	Changes from baseline at Week 48 in non-invasive disease-specific biomarkers, including but not limited to:  Collagen turnover (Pro-C3)  FIB-4  APRI  NFS  BARD score  FAST score  Agile 3+
•	To determine whether cotadutide is superior to placebo for weight reduction	•	Percent change from baseline in body weight at Week 48
•	To assess the effect of cotadutide versus placebo on glucose, adiponectin, and C-peptide	•	Change from baseline in fasting plasma glucose, adiponectin, and C-peptide at Week 48
•	To determine whether treatment with cotadutide compared with placebo will result in a reduction of BP	•	Change from baseline in SBP through Week 48

Resolution of NASH is defined as the absence of fatty liver disease or isolated simple steatosis without steatohepatitis and a NAS ballooning score of 0, inflammation score of 0 to 1, and steatosis score of any degree (from 0 to 3), as assessed by NASH Clinical Research Network/NAS score.

Improvement in fibrosis is defined as a one or more category improvement in the fibrosis category (NASH Clinical Research Network fibrosis stage) without worsening of NASH.

Worsening of NASH is defined as any increase in the ballooning, inflammation, or steatosis scores even if total NAS does not increase.

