### 4.2.3.2 Rationale for Exploratory Endpoints

The goal for therapies for NASH with fibrosis is to slow or reverse disease progression. However, rate of disease progression in NASH with fibrosis and event rates for liver outcomes require prolonged trial durations to evaluate and demonstrate improvements in liver outcome events. Histological features of NASH, including fibrosis, appear to have predictive value for liver outcomes and have been designated as surrogate endpoints of efficacy for novel NASH therapeutics. Therefore, improvements in histology-based endpoints in response to cotadutide treatment will be explored in this trial.

Currently applied manual methods of disease staging for NASH with fibrosis, particularly for staging of fibrosis, have limited sensitivity and reproducibility. AI-based methods are expected to provide improved sensitivity and reproducibility of histopathology reporting. AI-based histopathology assessments will be collected for all histology endpoints.

The endpoint on body weight will provide assessment of the beneficial effect of cotadutide on body weight in non-cirrhotic NASH with fibrosis and allow for correlation with improvement in NASH liver histology and other parameters related to metabolic control. Glycemic control as measured by HbA1c will be assessed in participants with T2DM as a high proportion of patients with NASH have comorbid T2DM. Evaluation of triglycerides will provide assessment of the beneficial effects of cotadutide on lipid profile in participants with NASH and attendant comorbidities.

Cotadutide is expected to lead to improvements in glucose and lipid homeostasis. Therefore, measures of metabolic homeostasis in circulation will be measured including but not limited to HbA1c, lipid profile, adiponectin, and C-peptide.

Although histology remains the preferred tool for diagnosis and assessment of treatment effects for NASH with fibrosis, given the invasive nature of a liver biopsy, there is a major unmet need to identify non-invasive tools that can reduce or replace the number of biopsies in

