# **3.3.1** General Study Level Definitions

#### 3.3.1.1 Definition of Baseline

Baseline biopsy specimen refers to either historical biopsies or on-study biopsies obtained during the screening period. Central pathology review of the eligibility read will occur upon baseline biopsy specimen receipt and processing at the histopathology vendor. Central pathology review results will support patient eligibility and enrollment. This is referred to as the eligibility read and will serve as the baseline for histology analyses.

For continuous endpoints, the baseline value for statistical analysis is the last non-missing value on or prior to date and time (if available) of administration of the first dose of IP. If multiple measurements occur on the same day, the last non-missing value on or prior to the time of first dosing of study drug will be considered as the baseline value. If these multiple measurements occur at the same time or the time is not available, the average of these measurements (for continuous data) will be considered as the baseline value. For electrocardiogram (ECG) parameters, the mean of the last set of triplicate measures prior to treatment is baseline.

For categorical endpoints, the last available record on or prior to the date of the first dose of study drug will be selected. If there are ties in terms of proximity to first dose, the value with the lowest severity will be selected (eg, normal will be selected over abnormal for safety ECG findings and '+' will be selected over '++' for urinalysis findings).

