## 4.2.3 Other Endpoints

#### 4.2.3.1 Definition

Tertiary/exploratory endpoints will be tested versus placebo at the 2-sided nominal alpha 5% level, without consideration of multiplicity:

The following are histological endpoints, to be assessed centrally 1) by independent pathologists and 2) by artificial intelligence, as detailed in the Central Histopathology Review

Charter. Analysis of continuous histological scores, if included, will be based solely on values provided by artificial intelligence.

- Proportion of participants with resolution of NASH without worsening of liver fibrosis based on biopsy at Week 48
- Proportion of participants with improvement of liver fibrosis by at least 1 stage without worsening of NASH based on biopsy at Week 48. (Worsening of NASH is defined as any increase in the ballooning, inflammation, or steatosis scores even if total NAS does not increase.)
- Proportion of participants with both resolution of NASH and improvement in fibrosis by at least 1 stage based on biopsy at Week 48
- Proportion of participants with improvement in fibrosis by at least 1 stage based on biopsy at Week 48
- Proportion of participants with improvement in NAS based on biopsy at Week 48
- Change from baseline in NAS based on biopsy at Week 48
- Change from baseline in fibrosis stage based on biopsy at Week 48
- Proportion of participants with progression, no change, or regression in fibrosis stage based on biopsy at Week 48
- Proportion of participants with improvement in key histological features of NASH on biopsy at Week 48, including:
  - Inflammation
  - Steatosis
  - Ballooning

Below are other exploratory/tertiary endpoints not based on biopsy:

- Change from baseline in liver enzymes including ALT and AST through Week 48
- Change from baseline in triglycerides, LDL cholesterol, and HDL cholesterol, non-HDL cholesterol, and total cholesterol, and HbA1c through Week 48
- Cotadutide PK exposure will be summarized and compared with prior data for consistency
- Change from baseline at Week 48 in:
  - LSM as assessed by FibroScan
  - Percentage CAP as assessed by FibroScan
- Changes from baseline at Week 48 in non-invasive disease-specific biomarkers, including but not limited to:
  - Pro-C3

- ELF score
- FIB-4
- APRI
- NFS
- BARD score
- FAST score
- Agile 3+
- Percent change from baseline in body weight at Week 48
- Change from baseline in FPG, adiponectin, and C-peptide at Week 48

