Change from baseline in continuous fibrosis scores from artificial intelligence, if available, will be analyzed by ANCOVA, as described above. Additionally, continuous scores from artificial intelligence for key histological features of NASH (inflammation, steatosis, ballooning), if available, may be analyzed using ANCOVA. Change from baseline in fibrosis stage (non-continuous scores) based on biopsy at Week 48 will not be analyzed by ANCOVA, but will instead be summarized descriptively by treatment using shift tables.

Analysis of continuous endpoints at multiple timepoints will be performed using MMRM adjusting for baseline value, fibrosis stage (F2/F3), T2DM status, analysis visit, treatment, the interaction of treatment and analysis visit and the interaction of baseline value and analysis visit. Only on-treatment data (Section 3.3.1) will be included in the model and missing data will not be imputed. An unstructured covariance structure will be used. If the computational algorithm fails to converge, the following structures will be tested in the following order:

Toeplitz, first-order autoregressive (AR[1]), and compound symmetry. Alternatively, covariates may be dropped from the model. Estimates, standard errors, and 95% confidence intervals of mean change from baseline or percent change from baseline will be reported by treatment and analysis visit. Restricted Maximum Likelihood estimation will be used in MMRM analyses.

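### Read literally, the SAP gives the categorical AI-scored histology endpoints a pathologist baseline, and AI-scored NASH resolution carries no baseline condition

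*SAP*

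**What the plan says.** SAP 3.3.1.1 describes the central pathologists' read that decides eligibility and then states: "This is referred to as the eligibility read and will serve as the baseline for histology analyses". It makes no exception for AI. The next paragraph has its own rule: "For continuous endpoints, the baseline value for statistical analysis is the last non-missing value on or prior to date and time" of first dosing. A third rule, for categorical endpoints, takes the last record up to the first dose and breaks ties towards the lowest severity.

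SAP 4.2.3.1 gives a single list of histological endpoints, "to be assessed centrally 1) by independent pathologists and 2) by artificial intelligence, as detailed in the Central Histopathology Review" Charter. It adds: "Analysis of continuous histological scores, if included, will be based solely on values provided by artificial intelligence". SAP 4.2.3.4 continues: "Change from baseline in continuous fibrosis scores from artificial intelligence, if available, will be analyzed by ANCOVA, as described above".

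Protocol 8.1.2 plans AI assessment for every histology endpoint based on NAS or fibrosis stage, at the time points of Section 1.3.

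The footnote to Table 8 in Protocol 3.1 defines resolution of NASH by the post-baseline scores: "a NAS ballooning score of 0, inflammation score of 0 to 1", with any steatosis score. SAP 4.2.3.2 derives it the same way. Neither places a condition on the baseline score. Protocol 5.1 requires NAS of at least 4 and at least 1 on each component at entry, as read by the central pathology review committee.

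**The concern.** Two separate gaps meet in the AI analyses.

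The first is the baseline. If the eligibility read is the baseline for every histology analysis, the categorical AI endpoints that need a baseline mix two instruments. A steady disagreement between AI and the pathologists on unchanged tissue would then be recorded as improvement or worsening. Protocol 4.2.3.2 introduces AI because manual methods, "particularly for staging of fibrosis, have limited sensitivity and reproducibility", so the sponsor itself expects the two reads not to be interchangeable.

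The second is resolution. On the pathologists' read nobody can be resolved at baseline, because entry requires ballooning of at least 1. Nothing imposes that on the AI read. A participant whom AI scores as ballooning 0 and inflammation 0 to 1 before the first dose can be an AI responder without any change.

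At stake is what the AI results mean: whether an AI responder is someone who changed, and whether AI and pathologist response rates can be set side by side.

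**Working it through.** **Baseline mismatch.** No arithmetic is needed. Take tissue that does not change, with each method repeating its own score:

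| Pathologist baseline | AI baseline (unused under the literal rule) | AI Week 48 | Recorded as |
|---|---|---|---|
| Ballooning 1 | 0 | 0 | Component improvement |
| F3 | F2 | F2 | Fibrosis improved by one stage |
| F2 | F3 | F3 | Fibrosis worsened; cannot count as resolution without worsening |

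The error can go either way. With an AI baseline, all three rows record no change.

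**Resolution: the plan's own figure first.** Protocol 9.2 gives 15% placebo response, a 20-point difference (so 35% active), about 100 per dose against 100 pooled placebo, two-sided 5%, and power above 90%.

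- Pooled rate: (0.15 + 0.35)/2 = 0.25.
- Null SE: √(2 × 0.25 × 0.75/100) = 0.0612.
- Alternative SE: √((0.15 × 0.85 + 0.35 × 0.65)/100) = 0.0596.
- Power: Φ((0.20 − 1.96 × 0.0612)/0.0596) = Φ(1.34) = 0.91.

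The stated figure is reproduced. It belongs to the design of 300 and is not specific to AI reads.

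**Resolution: an illustration.** Let q be the share that AI already scores as resolved at baseline. The documents do not give q, so a range is assumed. Apply 15% and 35% to the remaining participants, and suppose everyone AI-resolved at baseline is still so at Week 48 without AI fibrosis worsening. Then:

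- observed rate = q + (1 − q)p
- difference = (1 − q) × 20 points
- share of responders carried over from baseline = q / observed rate

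| q | Placebo | Active | Difference (points) | Carried over, placebo | Carried over, active |
|---|---|---|---|---|---|
| 0% | 15.0% | 35.0% | 20.0 | 0% | 0% |
| 5% | 19.3% | 38.3% | 19.0 | 26% | 13% |
| 10% | 23.5% | 41.5% | 18.0 | 43% | 24% |
| 20% | 32.0% | 48.0% | 16.0 | 63% | 42% |
| 30% | 40.5% | 54.5% | 14.0 | 74% | 55% |

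If only 90% stay resolved in each arm, the rate is 0.9q + (1 − q)p. At q = 10% that is 0.09 + 0.135 = 22.5% on placebo and 0.09 + 0.315 = 40.5% on active. The difference is still 18 points, and 0.09/0.225 = 40% of placebo responders are carried over. The difference does not depend on persistence as long as it is equal in both arms.

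**At the actual size.** About 55 randomized 2:1:2:1 gives 55/3 = 18.3 per dose and 18.3 pooled placebo. The same power formula, rough at this size, gives:

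| q | As written | Restricted to those not AI-resolved at baseline, n = 18.3(1 − q) |
|---|---|---|
| 0% | 0.28 | 0.28 |
| 10% | 0.21 | 0.26 |
| 20% | 0.16 | 0.23 |
| 30% | 0.13 | 0.21 |

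Power is low in every cell. The counts say more: at q = 10% about 18.3 × 0.235 = 4.3 placebo responders are expected, of whom 18.3 × 0.10 = 1.8 are carried over.

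**The case against.** The strongest defence is that a human baseline for AI change is an unlikely intention. The sentence in SAP 3.3.1.1 follows a description of the pathologists' eligibility read and does not mention AI. The protocol's objectives table describes AI-based assessment of changes from baseline, not only of Week 48 values, and SAP Section 2 reports no departure from the protocol other than the per-protocol set. AI reads are planned at the Section 1.3 time points, and the baseline biopsy material goes to the central laboratory. The Central Histopathology Review Charter, which is not among the documents, may name an AI baseline.

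This makes a same-method baseline plausible but does not settle it. SAP 4.2.3.2 says the vendor's data contain scores and not derived endpoints, so the baseline is applied under the SAP, and the SAP states one rule. The categorical rule does not help either, because it does not tell the analyst to match the reading method.

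A reader might infer four stronger things that the documents do not support:

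- *That every AI analysis uses the human baseline.* Continuous histology scores come from AI alone and plausibly fall under the separate continuous rule; a pathologist's stage cannot sensibly be their baseline.
- *That AI response is inflated in every arm.* Protocol 4.2.3.2 expects AI to be more sensitive and reproducible, not to score lower. If AI sees more ballooning or higher stages, mixed-method response could fall.
- *That the rule could produce a false treatment effect.* It applies alike to all randomized arms.
- *That correcting the baseline sentence would also correct resolution.* Resolution uses the baseline only through the fibrosis-worsening condition, so it needs its own provision.

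It is also fair that dropping AI-resolved participants from the main analysis would depart from the FAS and give AI and pathologist endpoints different denominators.

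**Conclusion.** The point holds in limited form. Followed to the letter, the SAP compares AI Week 48 scores with pathologist baseline scores for the categorical AI endpoints that need a baseline: fibrosis improvement, worsening of fibrosis or NASH, NAS change, component improvement and the fibrosis shift. This mixes method differences with change, in a direction that cannot be predicted from the documents.

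Separately, AI resolution can be met by participants already AI-resolved before dosing. The expected result is a diluted difference, by the factor 1 − q: 18, 16 or 14 points instead of 20 at q = 10%, 20% or 30%. These figures rest on an assumed q, on the planning rates holding for the remaining participants, and on equal persistence across arms. With q = 0 there is no effect.

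The endpoints are exploratory with nominal p-values, and safety is the primary objective, so no primary conclusion is affected. It should still be settled before unblinding, because it governs a complete second set of histology endpoints.

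**What to change.** In SAP 3.3.1.1, limit the eligibility read to the pathologist-scored endpoints and the analysis strata (SAP 3.3.1.3 already takes fibrosis stage from it). State that each AI-scored endpoint uses the AI read of the baseline biopsy as its baseline, and check that the charter says the same.

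In SAP 4.2.3, keep the FAS analysis of AI resolution as planned. Report for each arm the number who already meet the AI resolution criteria at baseline. Add a sensitivity analysis of AI resolution restricted to participants not AI-resolved at baseline. The restriction rests on a pre-dose characteristic, so it keeps the randomized comparison within that subset.

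The cost is a few lines of SAP text, one extra table, and a smaller denominator in the sensitivity analysis. This assumes that the AI reads planned at the Section 1.3 time points include the baseline slides, as the schedules suggest.

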# 3.3.1.2 Definition of On-study and On-treatment

All adverse events (AEs) with start date on or after the date of first treatment will be considered on-study. On-treatment AEs are those occurring within the on-study period and within + 7 days of treatment discontinuation. All AEs leading to discontinuation of IP will be considered on-treatment.

On-study assessments (eg, vital signs, clinical laboratory tests, ECG) are defined as those occurring after the date and time (if available) of administration of the first dose of IP. On-

treatment assessments are defined as those occurring within the on-study period and on or before the date of administration of the last dose of IP with the following windows following treatment discontinuation:

- Fasting plasma glucose (FPG): +1 day from treatment discontinuation.
- Biopsy, liver tests (alanine aminotransferase [ALT], aspartate aminotransferase [AST], total bilirubin [TBL], and alkaline phosphatase [ALP]), and disease-specific biomarkers: + 30 days from treatment discontinuation.
- All other efficacy and safety: +7 days from treatment discontinuation.

Assessments other than AEs recorded on the day of first treatment and with time unavailable for the assessment or for the first dose, will be considered to be not in the on-study/on-treatment periods. For listings of AEs, analysis phase will be indicated as on-treatment if the AE starts within the on-treatment period, as 'pre-treatment' if it starts prior to the on-treatment period, and as 'post-treatment' if it starts after the on-treatment period.

## 3.3.1.3 Analysis Strata

Randomization stratification variables (T2DM status and fibrosis stage) are used in analyses either as analysis strata or as covariates. Stratum according to Interactive Response Technology/Randomization and Trial Supply Management (IRT/RTSM) will not be used for primary analysis. Rather, analysis strata for primary analysis will be based on the electronic CRF (eCRF) value for T2DM status and the fibrosis stage in the eligibility read.

#### 3.3.1.4 Handling of Missing Dates

AE start and end date and concomitant medications (CMs) end date are imputed according to the rules described below. Start and end dates of treatment will not be imputed.

### 3.3.1.4.1 Imputation of AE End Date

Completely missing AE end dates are not imputed. Partial missing AE end dates are imputed as below:

- If the AE is ongoing, the end date is set to missing.
- If the AE is not ongoing, and if only the day is missing: Assume the last day of the collected month.
- If the AE is not ongoing, and both, the day and the month are missing: Assume 31-DEC of the collected year.

After applying these rules, if the imputed AE end date is after the end of study date, the AE is set to ongoing and the AE end date to missing.

#### 3.3.1.4.2 Imputation of AE Start Date

Before proceeding with the AE start date imputation, the AE end date is imputed if missing, as described in the previous section.

For completely missing start dates, impute as first dose date unless the end date is prior to the first dose date, in which case impute as 01-JAN-YYYY of the same year as the AE end date.

Partial dates are imputed as described below:

If the day is missing and the month and year are different from the month and year of the first dose of IP, assume 01-MMM-YYYY. If the month and year are the same as the first dose of IP month and year and the end date is on or after (including ongoing/missing) the first dose of IP, then assume the date of the first dose of IP. If the month and year are the same as the first dose of IP month and year and the end date is prior to the first dose of IP, then assume the end date.

If the month is missing and the year is different from the year of first dose of IP, assume 01-JAN-YYYY of the collected year. If the year is the same as the first dose of IP year and the end date is on or after (including ongoing/missing) the first dose of IP, then assume the date of the first dose of IP. If the year is the same as the first dose of IP and the end date is prior to the first dose of IP, then assume the end date.

After applying these rules, if the imputed AE start date is after a complete AE end date, then assume the same date as the complete AE end date; if the end date is missing and the imputed AE start date is after the end of study date, then assume the same date as the study end date.

#### 3.3.1.4.3 Imputation of Concomitant Medication End Date

Completely missing CM end dates (where the CM is not ongoing) are imputed as the date of last dose, unless contradicted by the CM start date, in which case the end date will be the same as the CM start date. Partial missing CM end dates are imputed as below:

- If the CM is ongoing, the end date is set to missing.
- If the CM is not ongoing, and if only the day is missing: Assume the last day of the of the collected month.
- If the CM is not ongoing and both the day and the month are missing: Assume 31-DEC of the collected year.

After applying these rules, if the imputed CM is after the end of study date, the CM is set to ongoing and the CM end date to missing.

